5.2 Exclusion Criteria

Subject will be excluded from participation in the study if any of the following apply:

1. Subject weighs < 45 kg at Screening.
2. Subject has received investigational therapy within 21 days prior to start of IP. (A subject with EGFR activating mutations or a subject with an ALK mutation is allowed to remain on an investigational EGFR TKI or ALK inhibitor until 4 days prior to initiation of IP administration.)
3. Subject requires or has received systemic steroid therapy or any other immunosuppressive therapy within 14 days prior to IP administration. Subjects using a physiologic replacement dose of hydrocortisone or its equivalent (defined as up to 30 mg per day of hydrocortisone, 2 mg per day of dexamethasone or up to 10 mg per day of prednisone) are allowed. Note: Corticosteroids for prophylaxis (e.g., contrast dye allergy) or for brief treatment of conditions not related to study treatment (e.g., delayed-type hypersensitivity reaction caused by a contact allergen) is also allowed.
4. Subject has symptomatic CNS metastases or subject has evidence of unstable CNS metastases even if asymptomatic (e.g., progression on scans). Subjects with previously treated CNS metastases are eligible, if they are clinically stable and have no evidence of CNS progression by imaging for at least 28 days prior to start of study treatment and are not requiring immunosuppressive doses of systemic steroids (> 30 mg per day of hydrocortisone, > 2 mg per day of dexamethasone or > 10 mg per day of prednisone or equivalent) for longer than 14 days.
5. Subject has leptomeningeal disease as a manifestation of the current malignancy.
6. Subject has an active autoimmune disease. Subjects with type 1 diabetes mellitus, stable endocrinopathies maintained on appropriate replacement therapy and skin disorders (e.g., vitiligo, psoriasis or alopecia) not requiring systemic treatment are allowed.
7. Subject was discontinued from prior immunomodulatory therapy due to a Grade \geq 3 toxicity that was mechanistically related (e.g., immune-related) to the agent in the judgment of the investigator.

8. Subject has known history of serious hypersensitivity reaction to a known ingredient of ASP1948 or severe hypersensitivity reaction to treatment with another monoclonal antibody.
9. Subject is positive for Hepatitis B virus (HBV) antibodies and surface antigen (including acute HBV or chronic HBV) or Hepatitis C virus ([HCV] RNA). Hepatitis C RNA testing is not required in subjects with negative Hepatitis C antibody testing. HBV antibodies are not required in subjects with negative Hepatitis B surface antigen (HBsAg).
10. Subject has received a live vaccine against infectious diseases within 28 days prior to initiation of study treatment.
11. Subject has a history of drug-induced pneumonitis (interstitial lung disease) or currently has pneumonitis.
12. Subject has an active infection requiring systemic therapy (e.g., intravenous antibiotics) within 14 days prior to IP treatment.
13. Subject is expected to require another form of antineoplastic therapy while on study treatment.
14. Subject has an uncontrolled intercurrent illness including, but not limited to cardiac arrhythmia or psychiatric illness/social situations that would limit compliance with study requirements.
15. Subject's AEs (excluding alopecia) from prior therapy have not improved to Grade 1 or baseline within 14 days prior to start of study treatment.
16. Subject has significant cardiovascular disease including:
 - Subject has inadequately controlled hypertension (defined as systolic blood pressure > 150 mmHg and/or diastolic blood pressure > 100 mmHg on antihypertensive medications).
 - Subject has a history of myocardial infarction or unstable angina within 6 months prior to Cycle 1 Day 1.
 - Subject has New York Heart Association Class II or greater chronic heart failure.
 - History of CVA or TIA within 6 months prior to study treatment.
 - Subject has significant vascular disease (e.g., aortic aneurysm requiring surgical repair or recent peripheral arterial thrombosis) within 6 months prior to study treatment.
17. Subject has a history of hemoptysis (bright red blood of 2 mL or more per episode) within 12 weeks prior to study treatment.
18. Subject has evidence of a bleeding diathesis or significant coagulopathy.
19. Subject has inadequate recovery from prior surgical procedure or has had a major surgical procedure, open biopsy or significant traumatic injury within 28 days prior to study treatment, or anticipates the need for a major surgical procedure during the course of the study or minor surgery within 7 days of starting study treatment.
20. Subject has initiated new treatment with medications that affect the coagulation cascade with an INR \geq 2 such as vitamin K antagonists, heparins and direct thrombin inhibitors or the use of factor Xa inhibitors within 28 days prior to the start of study treatment.

Note: If the subject started receiving such medications more than 28 days prior to the

- start of study treatment and needs to continue, this is allowed. However, new anticoagulation may not be initiated within 28 days prior to the start of study treatment.
21. Subject has any condition that, in the investigator's opinion, makes the subject unsuitable for study participation.

Waivers to the inclusion/exclusion criteria will **NOT** be allowed.

5.3 Restrictions During the Study

Not applicable.

5.4 Screen Failures

A screen failure is defined as a potential subject who signed the informed consent form (ICF), but did not meet 1 or more criteria required for participation in the study and was not enrolled.

For screen failures, the demographic data, date of signing the ICF, inclusion and exclusion criteria, AEs up to the time of screen failure and reason for screen failure will be collected in the electronic case report form (eCRF).

5.4.1 Rescreening

Results of screening assessments that do not meet the parameters required by eligibility criteria (e.g., clinical laboratory tests, vital signs, physical examination, electrocardiogram [ECG], etc.) may be repeated once within the 28-day screening period without the need to register the subject as a screen failure. If more than 28 days elapses from the date of signing the ICF, the subject must be documented as a screen failure. In order to rescreen, a new ICF must be signed and the subject entered into screening with a new subject identification number. Rescreening is only allowed once for an individual subject.

6 INVESTIGATIONAL PRODUCT(S)

6.1 Investigational Product(s) Administered

Table 7 Investigational Product

Name	ASP1948
Use	Test product
Dosage Formulation	Solution for injection
Physical Description	Clear colorless to slightly brown and/or yellow color
Unit Dose Strength	1200 mg (Q2W), 2000 mg (Q2W) and 3000 mg (Q3W)
Packaging and Labeling	[REDACTED] [REDACTED]
Route of Administration	Intravenous infusion
Administration Instruction	Administered intravenously over 60 minutes (-5 minute/+20 minute window). IP can be administered before or after meals.
IMP or Non-IMP	IMP
Sourcing	[REDACTED]

IMP: investigational medicinal product

Refer to the pharmacy manual for detailed information regarding preparation, handling and storage of the IP.

6.1.1 Investigational Product(s) Preparation and Administration

IP will be administered by trained and qualified healthcare professionals in an appropriately supervised healthcare institution setting. Medical equipment and supplies needed for potential IRRs (corticosteroids, epinephrine, antihistamines, intravenous fluids, aerosolized bronchodilators and oxygen, as well as intubation and tracheostomy equipment and a defibrillator) must be readily available in any area where IP is administered. Doses will be administered to the subjects via intravenous infusion using a calibrated infusion pump for the 3 dose levels, as outlined in [Table 8](#).

Table 8 Investigational Product Preparation and Administration

ASP1948 Dose	Number of Vials	Total Administration Volume	Apparatus
1200 mg	5	250 mL	250 mL intravenous bag
2000 mg	8	500 mL	500 mL intravenous bag
3000 mg	12	535 mL	500 mL intravenous bag

At the end of administration, flush with normal saline using 1 flush volume to ensure that the total diluted IP solution has been administered to the subject within the allowed administration window.

The start and stop times of IP infusion, including the flush time, will be documented. If the IP is interrupted due to an infusion reaction, such that the time from IP preparation exceeds 4 hours, then the administration must be discontinued.

Based on compatibility assessments, the acceptable materials for syringes, diluent infusion bags, infusion tubing and in-line or add-on filters are described in [Table 9](#).

Table 9 Product Contact Materials Tested and Concluded to be Compatible with ASP1948 Diluted in 0.9% Sodium Chloride Solution

Item	Material
Syringe	polypropylene
0.9% NaCl diluent intravenous bag (250 mL and 500 mL bags)	polyvinylchloride or polypropylene
Infusion tubing	polyethylene-lined polyvinylchloride/polyethylene, or polyvinylchloride
In-line or add-on filter (pore size of 0.2 to 0.22 µm)	polyethersulfone/polyethersulfone positively charged

NaCl: sodium chloride

6.1.2 Observation During and After Subject’s Dose of Investigational Product

In principle, subjects must be hospitalized from Cycle 1 Day 1 (first dose of ASP1948) to Cycle 2 Day 14 for Dose level A and Dose level B, or Cycle 1 Day 1 (first dose of ASP1948) to Cycle 1 Day 21 for Dose level C. If it is deemed possible to follow a subject on an outpatient basis based on his/her physical condition, etc. during the DLT observation period, the investigator must ensure his/her safety under outpatient management by performing the tests considered clinically necessary before discharge (observation and evaluation of general condition, blood tests, etc.). For the next 3 doses (third, fourth and fifth infusions for Dose level A and Dose level B or second, third and fourth infusions for Dose level C), subjects should remain at the site facility for at least 2 hours after completion of ASP1948 administration. The subject should be instructed to notify site personnel if he/she develops any AEs during this time period.

6.2 Preparation/Handling/Storage/Accountability

6.2.1 Packaging and Labeling

All IP used in this study will be prepared, packaged and labeled under the responsibility of qualified personnel at API or sponsor’s designee in accordance with API or sponsor’s designee standard operating procedures (SOPs), Good Manufacturing Practice (GMP) guidelines, International Council for Harmonisation of Technical Requirements for Pharmaceuticals for Human Use (ICH) GCP guidelines and applicable local laws/regulations.

Each carton and vial will bear a label conforming to regulatory guidelines, GMP and local laws and regulations that identifies the contents as investigational drug.

Refer to the pharmacy manual for detailed information regarding packaging and labeling of the IP.

6.2.2 Handling, Storage and Accountability

ASP1948 will be stored in a freezer at [REDACTED] *CCI* in a secure location until ready to use. ASP1948 should be protected from light. All unused vials must be kept in their original carton. After ASP1948 has been prepared for administration, the total storage time (combination of refrigeration and room temperature) should not exceed 24 hours, with a maximum time at room temperature of 4 hours. Refer to the pharmacy manual for additional information on IP handling.

The head of the study site or the test product storage manager should take accountability of the test product as following issues:

- The drug storage manager should store and take accountability of the IP as per the procedures for handling the IP written by the sponsor.
- The drug storage manager should prepare and retain records of the IP's receipt, inventory at the study site, use by each subject, and return of unused IP to the sponsor or alternative disposal. These records should include dates, quantities, batch/serial numbers, expiration dates (if applicable) and the unique code numbers assigned to the IP and subjects.
- The drug storage manager should prepare and retain records that document adequately that the subjects were provided the doses specified in the protocol and reconcile all IP supplied from the sponsor.

6.3 Randomization and Blinding

Not applicable.

6.4 Investigational Product Compliance

The dose and schedule of ASP1948 administered to each subject will be recorded on the appropriate form at every cycle. Reasons for dose delay, reduction or omission will also be recorded. This information, plus accountability for ASP1948 at every cycle will be used to assess compliance with the treatment.

Treatment compliance should be monitored closely and deviation in compliance should be reported to the sponsor.

6.5 Missed Doses

In the case that IP cannot be administered at a scheduled visit, it should be administered as soon as possible. Tumor assessments should continue as per protocol (every 8 weeks from Cycle 1 Day 1 for Dose level A and Dose level B, or every 9 weeks from Cycle 1 Day 1 for Dose level C) even if dosing is delayed. Subjects with infusion delays > 12 weeks from the end of prior treatment cycle should discontinue treatment and have an End of Treatment visit.

6.6 Previous and Concomitant Treatment (Medication and Nonmedication Therapy)

6.6.1 Previous Treatment (Medication and Nonmedication Therapy)

Previous treatment is defined as medications and therapies used before the start of study treatment.

The investigation period and items to be entered in the eCRF for previous treatment are shown below.

Previous Treatment	Investigation Period	Items to be Entered in the Electronic Case Report Form
Antitumor medications related to the primary cancer	Day of diagnosis of primary cancer to before the start of study treatment	Drug name, delivery route, duration of use, dose per administration, dose frequency, reason for premature discontinuation, and best overall response
Radiation therapy related to the primary cancer		Type of radiation therapy, area, and duration of use
Procedures related to the primary cancer		Name of procedure and date of use
All medications other than the above	28 days before the start of study treatment to before the start of study treatment	Drug name, delivery route, duration of use, and reason for use
All nonmedication therapies other than the above		Name of therapy, duration of use, and reason for use

6.6.2 Concomitant Treatment (Medication and Nonmedication Therapy)

Concomitant treatment is defined as medications and therapies used after the start of study treatment.

The investigation period and items to be entered in the eCRF for concomitant treatment are shown below. It is not necessary to enter concomitant treatment medications and therapies not used for direct therapeutic purpose, such as contrast media and diluents.

Concomitant Treatment	Investigation Period	Items to be Entered in the Electronic Case Report Form
New anticancer treatments for primary cancer	Start of study treatment to the end of safety follow-up (90 days from last dose) or until initiation of a new anticancer treatment, whichever comes first	Name of therapy, start date, and reason for use
All medications other than the above	Start of study treatment to the end of safety follow-up (30 days from last dose) or until initiation of a new anticancer treatment, whichever comes first	Drug name, delivery route, duration of use, and reason for use
All nonmedication therapies other than the above		Name of therapy, duration of use, and reason for use

- *Investigational agents:* The use of investigational agents is not allowed during study treatment.
- *Steroids and other immunosuppressive therapy:* The use of immunosuppressive agents and immunosuppressive doses of systemic steroids (> 30 mg/day of hydrocortisone, > 10 mg/day of prednisone, > 2 mg/day of dexamethasone or equivalent) is not allowed during study treatment unless needed to manage AEs related to study treatment. The use of topical, ocular, intra-articular, intranasal and inhaled corticosteroids (with minimal systemic absorption) is allowed. Physiologic replacement doses of systemic corticosteroids (\leq 30 mg/day of hydrocortisone or \leq 10 mg/day of prednisone or equivalent) are permitted. Corticosteroids for prophylaxis (e.g., contrast dye allergy) or for brief treatment of conditions not related to study treatment (e.g., delayed-type hypersensitivity reaction caused by a contact allergen) is also allowed.
- *Vaccines:* Live vaccines are prohibited while the subject is receiving study treatment and for 14 days after last dose of study treatment. Examples of live vaccines include, but are not limited to, the following: measles, mumps, rubella, chicken pox, yellow fever, Bacillus Calmette-Guerin (BCG) and typhoid vaccine.
- *Other Anticancer treatment:* The use of other anticancer therapy (e.g., chemotherapy, hormonal therapy, immunotherapy, radiotherapy, biological therapy and targeted therapy) is not allowed during study treatment; however, (1) subjects with mCRPC who do not have orchiectomy should continue ADT during the study and (2) subjects with breast cancer on endocrine or human EGFR 2 therapy should continue those therapies during the study.
 Palliative (limited field) radiation therapy for bone metastases is allowed. Study treatment should be interrupted during radiation therapy. The use of bisphosphonates and receptor activator of nuclear factor kappa-B ligand (RANK-L) inhibitors for bone metastases are allowed if initiated prior to study entry.
 Surgical treatment of isolated or symptomatic lesions for palliation or curative management is also allowed.

- *Other:* Hematopoietic factor products used for primary prevention (only prohibited during the DLT observation period).

6.7 Dose Modification

IP-related toxicity can result in the interruption or discontinuation of IP based on the discretion of the investigator.

6.7.1 Toxicities Requiring Permanent Discontinuation of ASP1948 Treatment

ASP1948 treatment will be permanently discontinued for the following toxicities that are assessed as related to ASP1948, if there is a reasonable possibility that the event may have been caused by ASP1948:

- Hematological toxicity requiring ASP1948 treatment interruption that does not recover to Grade 0 or 1 within 4 weeks
- AST or ALT $> 5 \times$ ULN (Grade ≥ 3) in subjects without liver metastases
- AST or ALT $> 8 \times$ ULN in subjects with liver metastases
- AST or ALT $> 3 \times$ ULN and TBL $> 2 \times$ ULN (in subject with Gilbert's syndrome: AST or ALT $> 3 \times$ ULN and direct bilirubin $> 1.5 \times$ ULN)
- TBL $> 3 \times$ ULN
- Grade ≥ 3 nonhematological AE except for Grade 3 rash that has improved to Grade 0 or 1 or Grade ≥ 3 endocrinopathies that are managed to Grade 0 or 1 with replacement therapy.
- Persistent Grade ≥ 2 AEs requiring ASP1948 interruption that do not recover to Grade 0 or 1 within 12 weeks after the last dose with steroid treatment tapered to physiological replacement doses (≤ 10 mg prednisone or equivalent) of study treatment. However, subjects with a persistent Grade ≥ 2 AE requiring ASP1948 interruption may continue on study treatment if asymptomatic and controlled, with investigator and sponsor agreement
- Grade ≥ 2 pneumonitis
- Guillain-Barré syndrome or myasthenic syndrome/myasthenia gravis
- Grade ≥ 2 encephalopathy, meningitis or Grade ≥ 2 motor or sensory neuropathy
- Any toxicity that results in the inability to reduce corticosteroid dose to 10 mg or less of prednisone or equivalent per day within 12 weeks
- Grade 3 or 4 IRRs

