- AST or ALT $> 3 \times$ ULN and TBL $> 2 \times$ ULN (in subject with Gilbert's syndrome: AST or ALT $> 3 \times$ ULN and direct bilirubin $> 1.5 \times$ ULN)
- TBL $> 3 \times$ ULN
- Grade ≥ 3 nonhematological AE except for Grade 3 rash that has improved to Grade 0 or 1 or Grade ≥ 3 endocrinopathies that are managed to Grade 0 or 1 with replacement therapy.
- Persistent Grade ≥ 2 AEs requiring ASP1948 interruption that do not recover to Grade 0 or 1 within 12 weeks after the last dose with steroid treatment tapered to physiological replacement doses (≤ 10 mg prednisone or equivalent) of study treatment. However, subjects with a persistent Grade ≥ 2 AE requiring ASP1948 interruption may continue on study treatment if asymptomatic and controlled, with investigator and sponsor agreement
- Grade ≥ 2 pneumonitis
- Guillain-Barré syndrome or myasthenic syndrome/myasthenia gravis
- Grade ≥ 2 encephalopathy, meningitis or Grade ≥ 2 motor or sensory neuropathy
- Any toxicity that results in the inability to reduce corticosteroid dose to 10 mg or less of prednisone or equivalent per day within 12 weeks
- Grade 3 or 4 IRRs

Toxicities Requiring ASP1948 Treatment Interruption

ASP1948 treatment will be withheld for the following toxicities if there is a reasonable possibility that the event may have been caused by ASP1948:

- Grade 4 neutropenia or Grade ≥ 3 febrile neutropenia
- Grade 4 thrombocytopenia or Grade 3 thrombocytopenia accompanied by bleeding that requires any transfusion
- Grade 4 anemia or Grade 3 anemia requiring transfusion
- Grade 3 rash or Grade 3 endocrinopathies
- AST or ALT ≥ 3.0 and $\leq 5.0 \times$ ULN or TBL > 1.5 and $\leq 3 \times$ ULN (in subject with Gilbert's syndrome: AST or ALT ≥ 3.0 and $\leq 5.0 \times$ ULN or direct bilirubin $> 1.5 \times$ ULN) in subjects without liver metastases
- AST or ALT ≥ 3.0 and $\leq 8.0 \times$ ULN or TBL > 1.5 and $\leq 3 \times$ ULN (in subjects with Gilbert's syndrome: AST or ALT ≥ 5.0 and $\leq 8.0 \times$ ULN or direct bilirubin $> 1.5 \times$ ULN) in subjects with liver metastases
- Any Grade 2 or higher irAE (including but not limited to those listed below):
 - colitis or diarrhea
 - hypophysitis
 - adrenal insufficiency
 - nephritis
 - ocular inflammatory toxicity

- pancreatitis
- new-onset neurological symptoms or signs (other than Grade 2 or higher encephalopathy, meningitis or Grade 2 or higher motor or sensory neuropathy, which require permanent discontinuation of ASP1948 treatment)
- IRR

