6.7.2 Toxicities Requiring ASP1948 Treatment Interruption

ASP1948 treatment will be withheld for the following toxicities if there is a reasonable possibility that the event may have been caused by ASP1948:

- Grade 4 neutropenia or Grade ≥ 3 febrile neutropenia
- Grade 4 thrombocytopenia or Grade 3 thrombocytopenia accompanied by bleeding that requires any transfusion
- Grade 4 anemia or Grade 3 anemia requiring transfusion
- Grade 3 rash or Grade 3 endocrinopathies

- AST or ALT ≥ 3.0 and $\leq 5.0 \times \text{ULN}$ or TBL > 1.5 and $\leq 3 \times \text{ULN}$ (in subject with Gilbert's syndrome: AST or ALT ≥ 3.0 and $\leq 5.0 \times \text{ULN}$ or direct bilirubin $> \text{ULN}$) in subjects without liver metastases
- AST or ALT ≥ 3.0 and $\leq 8.0 \times \text{ULN}$ or TBL > 1.5 and $\leq 3 \times \text{ULN}$ (in subjects with Gilbert's syndrome: AST or ALT ≥ 5.0 and $\leq 8.0 \times \text{ULN}$ or direct bilirubin $> \text{ULN}$) in subjects with liver metastases
- Any Grade 2 or higher irAE (including but not limited to those listed below):
 - colitis or diarrhea
 - hypophysitis
 - adrenal insufficiency
 - nephritis
 - ocular inflammatory toxicity
 - pancreatitis
 - new-onset neurological symptoms or signs (other than Grade 2 or higher encephalopathy, meningitis or Grade 2 or higher motor or sensory neuropathy, which require permanent discontinuation of ASP1948 treatment)
 - IRR

Additionally, ASP1948 treatment may be interrupted for any AE, laboratory abnormality or intercurrent illness that in the judgment of the investigator warrants delaying dosing of ASP1948.

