6.7.3 Criteria for Resuming Study Treatment

Dosing may be delayed for up to 12 weeks from the end of the prior treatment cycle for recovery of toxicity requiring IP treatment interruption. IP treatment may be resumed if the AEs have recovered to Grade 0 or 1 and steroid treatment tapered to physiological replacement doses (≤ 10 mg per day prednisone or equivalent) and do not meet the criteria for permanent discontinuation of study treatment. Interruption for COVID-19-related illness is limited to 12 weeks. Study treatment may be resumed in the absence of COVID-19-related symptoms per investigator judgement.

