Study Treatment Discontinuation

In the absence of an explanation for increased LFTs, such as viral hepatitis, preexisting or acute liver disease, presence of liver metastases, or exposure to other agents associated with liver injury, the subject may be discontinued from study treatment. The investigator may determine that it is not in the subject’s best interest to continue study treatment.

Discontinuation of study treatment should be considered if:

- AST or ALT $> 8 \times$ ULN
- AST or ALT $> 5 \times$ ULN for more than 2 weeks
- ALT or AST $> 3 \times$ ULN and† TBL $> 2 \times$ ULN or INR > 1.5) (if INR testing is applicable/evaluated)
- ALT or AST $> 3 \times$ ULN with the appearance of fatigue, nausea, vomiting, right upper quadrant pain or tenderness, fever, rash and/or eosinophilia ($> 5\%$)

† Samples taken simultaneously or within a maximum of 24 hours.

In addition, if close monitoring for a subject with moderate or severe hepatic laboratory tests is not possible, study treatment should be discontinued.

Hy's Law Definition:

1. Evidence that a drug can cause hepatocellular-type injury, generally shown by a higher rate than control of people with $3 \times$ AT elevations over the ULN ($2 \times$ elevations are too common in treated and untreated patients to be discriminating).
2. Cases of increased bilirubin (to at least $2 \times$ ULN) in people with concomitant AT elevation to at least $3 \times$ ULN (but it is almost invariably higher) and no evidence of intra- or extra-hepatic bilirubin obstruction (elevated ALP) or Gilbert's syndrome [Temple, 2006].

FDA Guidance for Industry titled "Drug-induced Liver Injury: Premarketing Clinical Evaluation" issued by the FDA on July 2009:

FDA Guidance for Industry:

1. The drug causes hepatocellular injury, generally shown by a higher incidence of 3-fold or greater elevations above the ULN of ALT or AST than the (nonhepatotoxic) control drug or placebo.
2. Among subjects showing such AT elevations, often with AT levels much greater than $3 \times$ ULN, 1 or more also show elevation of serum TBL to $> 2 \times$ ULN, without initial findings of cholestasis (elevated serum ALP).
3. No other reason can be found to explain the combination of increased AT and TBL, such as viral Hepatitis A, B or C; preexisting or acute liver disease; or another drug capable of causing the observed injury.

Reference

Temple R. Hy's Law: Predicting Serious Hepatotoxicity. *Pharmacoepidemiol Drug Saf.* 2006; 15(4):241-3.

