12.10 Guidelines for Management of Potential Immune-related Adverse Events

CTCAE Grade IrAE	Guidelines for Management
Grade 1	
 Continue ASP1948 and closely monitor the subject.
Grade 2	
 Withhold ASP1948 until toxicity improves to \leq Grade 1. Corticosteroids (initial dose of 0.5 to 1 mg/kg per day of prednisone or equivalent) may be administered. Taper corticosteroids over 4 to 6 weeks.
Grade 3	
 Withhold ASP1948 until toxicity improves to \leq Grade 1. Administer high-dose corticosteroids (prednisone 1 to 2 mg/kg per day or methylprednisolone intravenously 1 to 2 mg/kg per day). If symptoms do not improve with 48 to 72 hours of high-dose corticosteroids, infliximab may be administered. Taper corticosteroids over 4 to 6 weeks.
Grade 4	
 Stop ASP1948 immediately and permanently discontinue the subject.* Administer high-dose corticosteroids (prednisone 1 to 2 mg/kg per day or methylprednisolone intravenously 1 to 2 mg/kg per day) until toxicity improves to \leq Grade 1. Taper corticosteroids over 4 to 6 weeks.

CTCAE: National Cancer Institute Common Toxicity Criteria; IrAE: immune-related adverse event

*Subjects with controlled endocrinopathies with hormone replacement may resume ASP1948 under the discretion of the investigator.

Source: Brahmer JR, Lacchetti C1, Schneider BJ1, Atkins MB1, Brassil KJ1, Caterino JM, et al. Management of immune-related adverse events in patients treated with immune checkpoint inhibitor therapy: American Society of Clinical Oncology clinical practice guideline. J Clin Oncol. 2018;36(17):1714-68.

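### Permanent-stop and hold instructions for ASP1948 disagree in three places: immune-related events (Section 6.7 against Appendix 12.10), the Gilbert's bilirubin threshold, and the 12-week clock

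*Protocol*

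**What the plan says.** **Permanent stop.** Section 6.7.1 is mandatory: "ASP1948 treatment will be permanently discontinued for the following toxicities that are assessed as related to ASP1948". Its list includes a Grade 3 or higher "nonhematological AE except for Grade 3 rash that has improved to Grade 0 or 1", with a second exception for endocrinopathies controlled by replacement therapy. It separately lists "Grade ≥ 2 pneumonitis" and Grade 3 or 4 infusion-related reactions (IRRs). The synopsis carries the same stop list.

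**Hold.** Section 6.7.2 withholds for any immune-related AE (irAE) of Grade 2 or higher, with no upper grade. Its examples include colitis, nephritis, pancreatitis and IRR.

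**irAE management.** Appendix 12.10 gives dosing instructions by grade. At both Grade 2 and Grade 3 they begin "Withhold ASP1948 until toxicity improves to" Grade 1 or lower. Permanent discontinuation first appears at Grade 4. Appendix 12.9 lists pneumonitis among the potential irAEs.

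**Gilbert's syndrome.** The synopsis hold rule reads "direct bilirubin $> 1.5 \times$ ULN) in subjects without liver metastases". The same rule in Section 6.7.2 reads "direct bilirubin $> \text{ULN}$) in subjects without liver metastases". The mismatch recurs in the companion bullet for subjects with liver metastases.

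**Time limits.** Section 6.7.1 stops treatment for a persistent Grade 2 or higher AE that has not recovered within 12 weeks counted from the last dose. An exception covers asymptomatic, controlled events if investigator and sponsor agree. Section 6.7.3 says: "Dosing may be delayed for up to 12 weeks from the end of the prior treatment cycle for recovery of toxicity". Sections 6.5 and 8.1 also count from the end of the prior cycle.

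**The concern.** A mandatory stopping rule needs one reading. Here two people who each follow the protocol text can treat the same related event differently: one ends treatment, the other holds it and re-doses after recovery. The first consequence is for the subject's safety.

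The second is for the record. Major deviation PD2 (Section 10.3) applies to a subject who developed withdrawal criteria and was not withdrawn, but that section does not say which list supplies the criteria. A site that held and resumed after a Grade 3 colitis under Appendix 12.10 would meet a stop criterion under Section 6.7.1. Listed exposure and the number of AEs leading to withdrawal would also depend on which passage the site had followed.

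**Working it through.** The protocol states no figure to reproduce. The check sets the passages side by side for the same related event and computes the offset between the two clocks.

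**(a) irAEs**

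| Related event | 6.7.1 and synopsis stop list | 6.7.2 | Appendix 12.10 |
|---|---|---|---|
| Grade 3 colitis or nephritis | permanent stop | hold (no upper grade) | withhold; stop only at Grade 4 |
| Grade 2 pneumonitis | permanent stop | hold, as an irAE of Grade 2 or higher | withhold |
| Grade 3 IRR | permanent stop | hold (IRR listed, no upper grade) | not separately addressed |

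Section 6.7.2 does carve out Grade 2 or higher encephalopathy, meningitis and neuropathy as permanent stops. It makes no such carve-out for colitis, nephritis, pancreatitis or IRR.

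Is there an order of precedence?

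- Section 6.7.3 allows resumption only if no permanent-discontinuation criterion is met. That largely ranks 6.7.1 over 6.7.2, but it does not name Appendix 12.10.
- Section 2.3 directs the reader both to the Appendix 12.10 guidelines and to the protocol's own interruption and discontinuation instructions, without ranking them.
- The opening sentence of Section 6.7 leaves interruption or discontinuation to the investigator, so it does not rank them either.

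**(b) Gilbert's syndrome**

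Take direct bilirubin at 1.2 × ULN with transaminases below the hold range.

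- Section 6.7.2: 1.2 > 1, so hold.
- Synopsis: 1.2 is not above 1.5, so no hold.

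The two differ for every value above 1 and up to 1.5 × ULN.

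**(c) The 12-week clocks**

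Inputs: a limit of 12 weeks (6.7.1; 6.5, 6.7.3, 8.1) and cycle lengths of 14 days (Dose levels A and B) or 21 days (Dose level C) from Section 4.1.2. Assumption: the prior cycle is the one that began with the last dose.

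- 6.7.1: 12 × 7 = 84 days after the last dose.
- 6.7.3, Q2W: 14 + 84 = 98 days after the last dose; difference 98 − 84 = 14 days.
- 6.7.3, Q3W: 21 + 84 = 105 days after the last dose; difference 105 − 84 = 21 days.

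A subject whose event recovers on day 90 has passed the 84-day limit and meets a stop criterion, unless the asymptomatic-and-controlled exception is agreed. The same subject is still inside the permitted delay on either schedule. Because 6.7.3 bars resumption once a stop criterion is met, the last 14 or 21 days of its own window are closed to such a subject.

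**The case against.** The best defence is that Section 6.7 governs. Section 6.7.3 blocks resumption when a stop criterion is met, Appendix 12.10 is titled as guidelines and applied with investigator judgement, and its Grade 2 and 3 rows never say resume. This stands for most of the overlap between 6.7.1 and 6.7.2. It does not settle Appendix 12.10, which gives explicit ASP1948 instructions, contrasts withholding at Grade 3 with permanent stopping at Grade 4, and has no cross-reference to 6.7.1. Nor does it touch the Gilbert's mismatch.

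On the clocks, one can say that 6.7.1 limits recovery and 6.7.3 limits dosing delay, so both can be satisfied. They can, but 6.7.3 ties its delay to recovery from toxicity, and the gap therefore remains.

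A reader might infer more than the documents support:

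- *Transaminases above 5 and up to 8 × ULN with liver metastases* are held in 6.7.2 yet could fall under the general Grade 3 bullet in 6.7.1. If that bullet prevailed, the dedicated bullet for values above 8 × ULN with liver metastases would be void. Reading the specific over the general resolves this; it needs only a clarification.
- *Appendix 12.5* says "Discontinuation of study treatment should be considered if" certain liver limits are met. That is permissive monitoring guidance, and a site following 6.7.1 does not breach it.
- *DLT evaluability.* Related Grade 3 nonhematological events and Grade 2 pneumonitis are in general DLTs themselves (Section 4.1.4), and only subjects without a DLT can be excluded (Sections 4.1.5 and 9.2.5). The 12-week limits fall outside the 28- or 21-day window. One narrow route remains: a Gilbert's hold falling on Cycle 2 Day 1 at Dose level A or B.
- *The withdrawal table* counts actual withdrawals, so no passage has to govern it.
- *Frequency.* The 35 of 91 (38.5%) monotherapy patients with Grade 3 or higher events in Study 1948-CL-0101 are all-cause, while 6.7.1 covers related events only.

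**Conclusion.** The point holds for three inconsistencies, which differ in kind: stop against withhold for irAEs, hold against no hold in Gilbert's syndrome, and a 14-day (Q2W) or 21-day (Q3W) gap between time limits. It would be wrong to describe all three as stop against withhold.

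The number of subjects exposed is probably small. In Study 1948-CL-0101, irAEs of any grade occurred in 6 of 91 monotherapy patients (6.6%). In this study there were none among 9 patients at the 26 April 2021 cut-off. The case for acting rests on subject safety and on a major-deviation category that cannot be applied consistently, not on frequency. The PD2 exposure runs one way: a site that stops under 6.7.1 incurs none, while one that holds and resumes under Appendix 12.10 may.

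The DLT criteria and the BOIN decision table are not affected. The clock arithmetic rests on taking the prior cycle as the one begun by the last dose. Which rule is clinically right is not judged here.

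**What to change.** The sponsor's medical team should reconcile the synopsis (dose modification and treatment discontinuation), Sections 6.5, 6.7.1, 6.7.2, 6.7.3 and 8.1, and Appendix 12.10 into one consistent set of rules. In particular:

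1. State that Section 6.7 and Appendix 12.10 are to be read together, name the order of precedence, and say that it also determines PD2.
2. Give one direct-bilirubin hold threshold for Gilbert's syndrome in the synopsis and Section 6.7.2.
3. Give one starting point for the 12-week limits, or state how the recovery limit and the delay limit work together.

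As clarifications only, state how the general Grade 3 or higher bullet relates to the transaminase bullets for subjects with liver metastases, and that Appendix 12.5 is to be read with Section 6.7.1.

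The cost is protocol amendment text with the approvals that Appendix 12.1.3 requires. Sample size, the DLT rules and the planned analyses do not change. The clinical content is for the medical team; no threshold or rule is proposed.
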